13.9 Communicable Disease Reporting

Study staff will comply with local requirements to report communicable diseases identified among study participants to health authorities, including HIV-1. Participants will be made aware of reporting requirements during the informed consent process.

13.10 Access to HIV-related Care

13.10.1 HIV Counseling and Testing

HIV test-related counseling will be provided to all potential study participant mothers who consent to undergo HIV-1 screening to determine their eligibility for this study, and to all enrolled participants at each follow-up HIV-1 testing time point. Testing will be performed in accordance with the algorithms in Appendices [III](#) and [IV](#). Counseling will be provided in accordance with standard HIV counseling policies and methods at each site and additionally will provide information regarding the known efficacy of the study products in preventing HIV-1 infection. In accordance with the policies of the NIH, participants must receive their HIV-1 test results to take part in this study. Condoms will be offered to participants throughout the duration of their participation.

13.10.2 Care for Participants Identified as HIV-Infected

Care for participants identified as HIV-infected is described in [Section 9.5](#).

13.11 Study Discontinuation

This study may be discontinued at any time by NIH, the MTN, IPM, Gilead Sciences, Inc., the US FDA, the US OHRP, other local or international government or regulatory authorities, or site IRBs/ECs.

14 PUBLICATION POLICY

DAIDS/NIAID and MTN policies and a CTA between IPM, Gilead Sciences, Inc., and NIAID, will govern publication of the results of this study. Any presentation, abstract, or manuscript will be submitted by the Investigator to the MTN Manuscript Review Committee, DAIDS/NIAID, NICHD, National Institute of Mental Health (NIMH), IPM and Gilead for review prior to submission.

15 APPENDICES

APPENDIX I: Table of Visits and Study Procedures – Mothers

	Visit 1 SCR	Visit 2 ENR	Visits 3,4 (Week 1, 2)	Visits 5, 6 (Month 1, 2)	Visit 7 (Month 3 PUEV)	Visit 8 SEV (2 weeks after PUEV)	Early Termination Visit
ADMINISTRATIVE AND REGULATORY							
Obtain/confirm informed consent	^	X					
Assess and/or confirm eligibility	X	X					
Collect demographic information	X						
Randomization		X					
Collect/review/update locator information	X	X	X	X	X	X	X
Assign a unique PTID number	X						
Obtain signed medical records release and pediatric care provider information	X						
Provide reimbursement	X	X	X	X	X	X	X
Schedule next visit/contact	*	*	X	X	X	*	*
BEHAVIORAL							
HIV pre-/post-test counseling	X	X	*	X	X		X
HIV/STI risk reduction counseling	X	X	*	X	X	*	X
Contraception counseling	X	X	*	X	X	X	X
Behavioral assessment		X	X	X	X		X
Product acceptability assessment		X	X	X	X		X
Protocol adherence counseling		X	X	X	X		
Social harms assessment			X	X	X	X	X
In-depth interview (IDI) (subset)					♦		X
PrEP counseling						X	X
CLINICAL							
Infant feeding assessment	X	X	X	X	X		X
Concomitant medications and vaginal products	X	X	X	X	X	X	X
Review/update medical history	X	X	X	X	X	X	X
Physical exam (Targeted after Screening Visit)	X	X	*	*	X	*	X
Pelvic exam	X	X	*	*	X	*	X
Collect AEs	*	▼	*	X	X	X	X
Treat STIs/RTI/UTI	*		*	*	*	*	*

		Visit 1 SCR	Visit 2 ENR	Visits 3,4 (Week 1, 2)	Visits 5, 6 (Month 1, 2)	Visit 7 (Month 3 PUEV)	Visit 8 SEV (2 weeks after PUEV)	Early Termination Visit
Disclose available test results		X	X	X	X	X	X	X
LABORATORY								
URINE	Pregnancy test	X	X	*	*	X	*	X
	Urine dipstick and/or culture	*	*	*	*	*	*	*
BLOOD	HIV-1 testing	X	X	*	X	X	*	X
	AST/ALT	X		*	*	X	*	X
	Creatinine clearance	X		*	*	X	*	X
	Complete blood count (CBC) with platelets	X		*	*	X	*	X
	Syphilis serology	X	*	*	*	*	*	*
	Plasma archive		X					
	HBsAg	X						
	Plasma for DPV drug levels (DPV group)			X	X	X	X	X
	DBS for FTC-TP & TFV-DP drug levels (Truvada group)		X (Both DPV & Truvada groups)	X	X	X	X	X
BREAST MILK	Breast milk for DPV drug levels (DPV group)			X	X	X	X	X
	Breast milk for FTC and TFV drug levels (Truvada group)			X	X	X	X	X
PELVIC	NAAT (GC/CT/TV)	X	*	*	*	*	*	*
	Wet prep/KOH wet mount for candidiasis and/or BV	*	*	*	*	*	*	*
	Vaginal pH	*	*	*	*	*	*	*
	Vaginal swab(s) for microbiota		X			X		X
	Vaginal Gram stain		X			X		X
	Vaginal swab(s) for biomarkers		X			X		X
STUDY PRODUCT	Adherence Assessment: Returned study VR				X	X		X
STUDY PRODUCT								
Provide study VR or study tablets			X		X			

	Visit 1 SCR	Visit 2 ENR	Visits 3,4 (Week 1, 2)	Visits 5, 6 (Month 1, 2)	Visit 7 (Month 3 PUEV)	Visit 8 SEV (2 weeks after PUEV)	Early Termination Visit
Provide product use instructions		X		X			
Insertion/removal of study VR at the clinic (clinician to check VR placement) or DOD of first study tablets		X		X			
Remove and/or collect study VR or unused study tablets				X	X		X
Offer male condoms	X	X	X	X	X	X	X

[^] Informed consent can be separate or combined for Screening & Enrollment; depending upon site criteria

* If indicated and/or per local standard of care

▼ Enrollment delayed until symptoms resolved if treatment is indicated

◆ May be scheduled any time between PUEV and SEV

APPENDIX II: Table of Visits and Study Procedures – Infants

[figure not shown]
	Visit 1 SCR	Visit 2 ENR	Visits 3,4 (Week 1, 2)	Visits 5, 6 (Month 1, 2)	Visit 7 Month 3 (PUEV)	Visit 8 SEV (2 weeks after PUEV)	Early Termination Visit
ADMINISTRATIVE AND REGULATORY							
Obtain/confirm informed consent	^	X					
Assess and/or confirm eligibility	X	X					
Collect demographic information	X						
Assign a unique PTID number	X						
CLINICAL							
Review pediatric care records	▲	X	X	X	X	X	X
Review/update concomitant medications	X	X	X	X	X	X	X
Review/update medical history	X	X	X	X	X	X	X
Physical exam (Targeted after Screening Visit)	X	X	*	*	X	*	X
Collect AEs			X	X	X	X	X
LABORATORY							
Plasma for DPV drug levels (DPV group)			X (V4 only)	X	X	X	X
DBS for FTC-TP and TFV-DP drug levels (Truvada group)			X (V4 only)	X	X	X	X

[^] Informed consent can be separate or combined for Screening & Enrollment; depending upon site criteria

[figure not shown]
* If indicated and/or per local standard of care

▲ Review pediatric care records as available once all required permissions have been obtained

1. LIST OF ABBREVIATIONS AND ACRONYMS

A list of abbreviations used in the SAP.

Term/Abbreviation	Definition
AE	Adverse Event
AIDS	Acquired Immunodeficiency Syndrome
ALT	Alanine Aminotransferase
AST	Aspartate Aminotransferase
AUC	Area Under the concentration Curve
CASI	Computer assisted self-interview
CBC	Complete Blood Count
CI	Confidence Interval
C _{max}	Maximum Concentration
CRF	Case Report Form
CV	Coefficient of Variation
CVF	Cervicovaginal Fluid
CT	Chlamydia trachomatis
DAIDS	Division of AIDS
DBS	Dried blood spot
DPV	Dapivirine
EAE	Expedited Adverse Event
eCRF	Electronic Case Report Form
FTC	Emtricitabine
FTC-TP	Emtricitabine triphosphate
GC	Neisseria gonorrhoeae
GM	Geometric Mean
HIV	Human Immunodeficiency Virus
HSV	Herpes Simplex Virus
IDI	In-depth Interview
IQR	Interquartile Range
IRB/EC	Institutional Review Board/ethics committee
IVR	Intravaginal Ring
ITT	Intent to treat
LLOQ	Lower limit of quantification

MCV	Mean corpuscular volume
MedDRA	Medical dictionary for regulatory activities
MTN	Microbicide Trials Network
NAAT	Nucleic acid amplification test
PD	Pharmacodynamics
PEP	Post-exposure prophylaxis
PK	Pharmacokinetics
PrEP	Pre-exposure prophylaxis
PUEV	Product use end visit
SA	South Africa
SAE	Serious Adverse Event
SAP	Statistical Analysis Plan
SCHARP	Statistical Center for HIV/AIDS Research and Prevention
SD	Standard Deviation
SDMC	Statistical Data Management Center
SMC	Study Monitoring Committee
SRA	Statistical Research Associate
STIs	Sexually Transmitted Infections
TDF	Tenofovir disoproxil fumarate
TFV	Tenofovir
TFV-DP	Tenofovir diphosphate
T _{max}	Time to Reach the Maximum Concentration
TV	Trichomonas vaginalis
VR	Vaginal ring
WBC	White blood cell

2. INTRODUCTION

This Statistical Analysis Plan (SAP) document covers the final analysis of MTN-043. The analysis of primary and secondary endpoints with supporting summaries are included. Some selected exploratory endpoint analyses are also be included.

2.1 General Design Considerations

Short Title: B-PROTECTED: Mother-Infant Pair Study of Dapivirine Ring and PrEP in Breastfeeding

Clinical Phase: Phase 3B

IND Sponsor: DAIDS

Funders:	Division of AIDS, NIAID, NIMH, NICHD, US NIH
Protocol Chair:	[name], MMed, MPH
Protocol Co-Chairs:	[name], CNM [name], MPH
Sample Size:	Approximately 200 mother-infant pairs
Study Population:	Healthy, HIV-uninfected breastfeeding women and their healthy infants between 6 and 12 weeks old (inclusive) at the time of enrollment
Study Sites:	
 • Blantyre, Malawi • Kampala, Uganda (MU-JHU) • Shandukani, South Africa (Wits RHI) • Zengeza, Zimbabwe
Study Hypotheses:	
 • Maternal exposure to study products will be safe for mothers and their breastfeeding infants. • Dapivirine (DPV) will be detectable at low levels in breast milk of participant mothers using the vaginal ring (VR). • Emtricitabine (FTC) and tenofovir (TFV) will be detectable at low levels in breast milk of participant mothers taking Truvada. • DPV will be detectable in the blood of some breastfeeding infants. • Emtricitabine triphosphate (FTC-TP) and/or tenofovir diphosphate (TFV-DP) will be detectable in the blood of some breastfeeding infants.
Study Design:	Phase 3B, randomized, open-label, multi-site, mother-infant pair safety and drug detection study, with 12 weeks of planned study product exposure to either DPV VR (25 mg) or oral Truvada tablet (200 mg emtricitabine [FTC]/300 mg tenofovir disoproxil fumarate [TDF]).
Study Duration:	Each enrolled mother-infant pair will be followed for approximately three and a half months (14 weeks).
	Note: If a mother seroconverts on study, her infant will have an additional visit, 12 weeks after seroconversion is diagnosed, for additional HIV testing.
Study Products:	
 • Silicone elastomer matrix VR containing 25 mg of DPV • Oral tablets (Truvada) containing 200 mg FTC/300 mg TDF
Study Regimen:	Mother-infant pairs will be randomized to the above study products in a 3:1 ratio (VR: tablet). For mothers randomized to the DPV VR, the VR will be worn continuously for approximately one month (4 weeks), to be replaced monthly (4 weeks) for approximately three months (12 weeks). Mothers using Truvada tablet will take one tablet by mouth daily for approximately three months (12 weeks).

2.2 Study Objectives and Endpoints

Primary Objectives:

Maternal Safety Outcomes: To describe the maternal safety profile associated with study product exposure during breastfeeding in both study arms.

Infant Safety Outcomes: To describe the infant safety profile associated with study product exposure during breastfeeding in both study arms.

Drug Detection: To summarize the frequency of study drug detection and concentration of study drug(s) in mothers and their breastfeeding infants.

Primary Endpoints:

Maternal safety (composite)

- All serious adverse events (SAEs) including maternal deaths in both study arms
- All Grade 3 or higher adverse events (AEs) as defined by the *Division of AIDS (DAIDS) Table for Grading the Severity of Adult and Pediatric Adverse Events, Corrected Version 2.1, July 2017 and/or Addendum 1 (Female Genital Grading Table for Use in Microbicide Studies [Dated November 2007])* in both study arms

Infant safety (composite)

- All SAEs including infant deaths in both study arms
- All Grade 3 or higher AEs as defined by the *Division of AIDS (DAIDS) Table for Grading the Severity of Adult and Pediatric Adverse Events, Corrected Version 2.1, July 2017* in both study arms

Drug Detection

- Maternal plasma DPV concentrations
- Maternal blood FTC-TP and TFV-DP concentrations
- Maternal breast milk DPV concentrations
- Maternal breast milk FTC and TFV concentrations
- Infant plasma DPV concentrations
- Infant blood FTC-TP and TFV-DP concentrations

Secondary Objectives:

Adherence: To characterize adherence to open-label use of the DPV VR (25 mg) and oral Truvada in breastfeeding women.

Acceptability: To characterize acceptability of open-label use of the DPV VR (25 mg) and oral Truvada in breastfeeding women.

Secondary Endpoints:

Adherence

- Participant report of frequency of study product use (e.g., missed doses for oral Truvada and VR removal/expulsions [voluntary and involuntary] and duration without VR in vagina)
- Residual drug levels in returned VRs
- Maternal plasma DPV concentrations
- Maternal blood FTC-TP and TFV-DP concentrations

Acceptability

- Self-reported attitudes about study product attributes and willingness to use their assigned study product during breastfeeding in the future
- Proportion of participants who find their study product to be at least as acceptable as other HIV prevention methods

2.3 Randomization

Participants were randomized in a 3:1 ratio (VR:tablet) to the two arms of the study stratified by study site. The randomization scheme was generated and maintained by the MTN SDMC.

2.4 Blinding

MTN-043 is an open label study. The study product assignments were not blinded.

2.5 Sample Size and Power

The target sample size was 200 mother-infant pairs randomized 3:1 to vaginal ring vs oral Truvada. A total of 197 mother-infant pairs were enrolled. The sample size is based upon feasibility, anticipated low drug concentrations, and the likelihood of a favorable safety profile. The statistical properties of the study are described using the probability of observed safety events defined in the primary endpoint. The probabilities of observing a safety event for various “true” event rates were calculated. For example, if the true safety event rate was 5%, the probability of observing zero safety events is 0.05% for the cohort size of 150 participants (DPV VR) and is 7.69% for cohort size of 50 participants (Truvada). An alternative way of describing the statistical properties is in terms of 95% confidence interval. For example, if none of the participants experience a safety event, the 95% exact 2-sided upper confidence bound for the true event rate is 2.43% for participant receiving the VR regimen and is 7.11% for participants receiving Truvada. The properties above also inform the hypotheses around drug detection where number of events is the number of participants with detectable drug levels. Further details of the statistical properties for this study are described in section 10.5 of the protocol.

3. GENERAL DATA ANALYSIS CONSIDERATIONS

3.1 Analysis Set(s)

Following the intent to treat (ITT) approach, participants will be classified by their randomized study arm regardless of the study product received. Participants found to be ineligible post-enrollment will be excluded from all analyses. For the primary safety endpoints (maternal safety, infant safety) participants enrolled and who received at least one dose of study product will be included. All participants with at least one post-enrollment drug concentration result will be included in the primary analysis for drug detection.

For analysis of drug concentrations, a secondary analysis will be conducted including only visits in which a participant has been exposed to the study product and excluding visits of mothers or infants with mothers terminating the study early or on product hold.

For the secondary endpoint of adherence, all mothers will be included. However, reasons for study product non-use from all mothers will be tabulated. A secondary sensitivity analysis will be conducted including only mothers with drug concentration results for at least one visit after Enrollment.

For the secondary endpoint of acceptability, all mothers with non-missing responses for the acceptability and preference questions (#1, #2, #5, #6 and #7) on the Behavioral Assessment – Month 3 Follow Up

eCRF will be included. Mothers with some missing responses to the identified questions will be included in each part of the acceptability analysis as appropriate.

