7.3 Visit 2: Enrollment Visit (Day 0)

The Enrollment Visit must be completed within 35 days of the Screening Visit. Enrollment for the mother and infant must occur at the same visit.

Table 5: Visit 2 – Enrollment Visit - Mothers

Visit 2 – Enrollment Visit - Mothers	
Component	Procedures
Administrative and Regulatory	
 Re-assess and confirm eligibility Review/confirm informed consent Randomization Review/update locator information Provide reimbursement Schedule next visit/contact*
Behavioral/Counseling	
 Baseline behavioral assessment Product acceptability assessment HIV pre- and post-test counseling HIV/STI risk reduction counseling Protocol adherence counseling Contraception counseling
Clinical	
 Review/update medical history Infant feeding assessment Review/update concomitant medications and vaginal products Targeted physical exam Pelvic exam Treat RTI/UTI/STIs▼ Disclose available test results

Visit 2 – Enrollment Visit - Mothers		
Component		Procedures
Laboratory	Urine	
 • Urine dipstick and/or culture* • Pregnancy test
	Blood	
 • HIV-1 testing • Syphilis serology* • Plasma archive • Dried blood spot (DBS) for baseline FTC-TP & TDF-DP drug levels (DPV & Truvada groups)
	Pelvic	
 • NAAT for GC/CT/TV* • Wet prep/KOH wet mount for candidiasis and/or BV* • Vaginal pH* • Vaginal swab(s) for microbiota • Vaginal Gram stain • Vaginal swab(s) for biomarkers
Study Product/Supplies		
 • Provide study VR or study tablets • Insertion of study VR at the clinic (clinician to check VR placement) or DOD of first study tablet • Provide product use instructions • Offer male condoms

* If indicated and/or per local standard of care

▼ Enrollment delayed until symptoms resolved if treatment is indicated

Table 6: Visit 2 – Enrollment Visit - Infants

Visit 2 – Enrollment Visit - Infants		
Component		Procedures
Administrative and Regulatory		
 • Re-assess and confirm eligibility • Review/confirm informed consent
Clinical		
 • Review/update medical history • Review pediatric care records • Review/update concomitant medications • Targeted physical exam

* If indicated and/or per local standard of care

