8.3 Adverse Events Definitions and Reporting Requirements

8.3.1 Adverse Events

An AE is defined as any untoward medical occurrence in a clinical research participant administered an investigational product and which does not necessarily have a causal relationship with the investigational product. As such, an AE can be an unfavorable or unintended sign (including an abnormal laboratory finding, for example), symptom or disease temporally associated with the use of an investigational product, whether considered related to the product. This definition is applied to all study participants at the time of enrollment. This definition is applied to all study groups and is applied beginning at the time of enrollment (i.e., once a participant is randomized). The term “investigational product” for this study refers to the DPV VR and Truvada oral tablet.

Study participants will be provided instructions for contacting the study site to report any untoward medical occurrences they may experience. In cases of potentially life-threatening events, participants will be instructed to seek immediate emergency care. Where feasible and medically appropriate, participants will be encouraged to seek evaluation where a study clinician is based, and to request that the clinician be contacted upon their arrival. With appropriate permission of the participant, whenever possible, records from all non-study medical providers related to untoward medical occurrences will be obtained and required data elements will be recorded on study CRFs. All participants reporting an untoward medical occurrence will be followed clinically until the occurrence resolves (returns to baseline) or stabilizes.

Study site staff will document in source documents and in the study database all AEs reported by or observed in enrolled study participants, regardless of severity and presumed relationship to study product.

AE severity and laboratory tests will be graded per the *DAIDS Table for Grading the Severity of Adult and Pediatric Adverse Events, Corrected Version 2.1, July 2017* and *Addendum 1, (Female Genital Grading Table for Use in Microbicide Studies; dated November 2007)*. In cases where a genital AE is covered in both tables, the *Female Genital Grading Table for Use in Microbicide Studies* will be the grading scale utilized.

The following will not be reportable as AEs:

- Asymptomatic BV and asymptomatic vulvovaginal candidiasis.

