10.8.2 Primary Analyses

An intent to treat analysis will be performed to summarize the frequency of primary endpoints (maternal safety, infant safety and drug detection) by study arm. A secondary analysis will be conducted including only visits in which a participant has been exposed to the study product. Consistent with the primary objectives to describe the safety profile and drug detection in each arm, the number and the percentages of participants experiencing each primary endpoint (see [Section 10.2](#)) will be tabulated by study arm. Each participant will contribute once in each category (i.e., only for highest severity AE for each participant) for the calculation of event rates. Exact binomial confidence intervals will be calculated for each primary endpoint. A secondary analysis will be performed to summarize the total number of primary and secondary safety endpoints reported per participant by study arm.

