12. CHANGE HISTORY

Identify major changes. Only changes after version 1.0 approval need to be recorded.

Version		Affected Section(s)	Activity Description
Number	Effective Date		
2.0	Nov. 4, 2022	Title page, ToC, Sections 1, 2.3, 3.1, 3.2, 5, 6.1, 6.2, 8, 8.3, 9.1, 9.2, 10, 10.1, 10.4, 10.7.	
 - Added an effective date on title page per SCHARP guidelines - Updated Table of Contents - Clarified that the intent to treat (ITT) approach is not a modified ITT and provided more detail of participants included in the analysis. Changes made in the acronyms section 1.0 and sections 3.1, 3.2, and 8. - Removed the ambiguous text about less informative imputation in section 3.2. - Changed to summaries with the number of non-missing values rather than the number of missing values as described in section 5. - In section 6.1, a reference to section 3.1 was added. - Clarified that infant consent was made by the infant's mother in section 6.3. - To section 8.3, added arithmetic mean, standard deviation, and number of detectable drug levels to drug concentration summaries. The natural log transformations will not be used but figures will be presented using the log scale. Box plots with medians will be used to present drug concentrations over study timepoints. - Provided specific details for secondary adherence endpoint analysis description in section 9.1. Adherence defined as "no use" (rather than "consistent study product use") with identified cut-points for the study products. Dapivirine (DPV) release rate defined for the DPV ring arm. Further details provided for the comparison (GEE) models. Added an explanation of the differences from the protocol. - Clarified that Questions #1 and #2 are study product arm specific. - Removed first sentence of section 10 with clarification provided in section 3.1. - In sections 10.1 and 10.4, clarified that number and percentages of participants with AEs or abnormal pelvic exam findings will be included in addition to the number and percentages of AEs or pelvic exam findings in the summaries. - In section 10.7, text for "Genital Infections" and "other vaginal findings" was added for clarification. - Made grammatical and typographical error corrections (2.3, 3.1, 6.2, 8.3)

From: [[name]](#)
To: [[name]](#)
Subject: RE: MTN043 SAP version 2.0 approval
Date: Thursday, October 20, 2022 4:06:59 PM

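### SAP 3.1 excludes participants found ineligible after enrollment from all analyses, with no exemption for those already dosed, against the SAP's own at-least-one-dose safety set and the protocol's intent-to-treat analysis

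*SAP*

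**What the plan says.** SAP 3.1 defines the analysis sets in consecutive sentences. The first is about assignment: "Following the intent to treat (ITT) approach, participants will be classified by their randomized study arm regardless of the study product received". The second is the sentence at issue: "Participants found to be ineligible post-enrollment will be excluded from all analyses". It carries no exception for someone who has already received product, and it does not limit the decision to information from before randomization. The third defines the primary safety set on a different basis: "participants enrolled and who received at least one dose of study product will be included". The drug detection set is then everyone with at least one concentration result after enrollment.

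Protocol 10.8.2 says: "An intent to treat analysis will be performed to summarize the frequency of primary endpoints". It names maternal safety, infant safety and drug detection, and mentions no removal for ineligibility. Elsewhere, SAP 7 describes baseline in everyone enrolled, and SAP 9.1 analyses adherence in all mothers. SAP 9.1 also lists how the adherence analysis departs from the protocol. Nothing comparable is said about the exclusion in 3.1.

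On timing, protocol 7.3 (Table 5) places the first exposure at the Enrollment Visit itself: "Insertion of study VR at the clinic (clinician to check VR placement) or DOD of first study tablet". Protocol 8.3.1 says the adverse event definition "is applied beginning at the time of enrollment (i.e., once a participant is randomized".

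**The concern.** The primary objectives are to describe safety in mothers and infants exposed to the products. A participant whose ineligibility comes to light after enrollment will normally have been dosed, or be the infant of a dosed mother. Read literally, the exclusion takes that person out of the primary safety rates, and out of the adverse event tables and listings in SAP 10.1. No planned analysis puts the person back.

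The exclusion need not be unrelated to outcome. Several criteria rest on investigator judgement: that the infant is generally healthy (protocol 5.2.2), and that neither mother nor infant has a condition that would be unsafe or would complicate interpretation of the results (protocol 5.3.1 and 5.3.2). An infant illness that declares itself after dosing could lead to the view that the infant should not have been enrolled. Assignment is known to everyone (SAP 2.4), so that view could be formed with both arm and event in sight. This needs no bad faith; the rule simply permits it.

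**Working it through.** **Step 1: set the rules side by side.** Take a mother who is randomised, dosed at the Enrollment Visit and later found ineligible.

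| Source | Is she analysed? |
|---|---|
| SAP 3.1, second sentence | No, in any analysis |
| SAP 3.1, third sentence (primary safety) | Yes: enrolled and dosed |
| SAP 3.1, drug detection set | Yes, if she has one result after enrollment |
| SAP 7 (baseline) | Yes: all enrolled |
| SAP 9.1 (adherence) | Yes: all mothers |
| Protocol 10.8.2 (primary) | Yes, under intent to treat; no exclusion stated |

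The SAP gives no order of precedence. One analyst could keep her and another drop her, each following the text.

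**Step 2: reproduce the plan's own figures.** SAP 8.1 and 8.2 use exact binomial 95% limits, and SAP 5 names the Clopper-Pearson method. For x events in n, the lower limit is the 0.025 quantile of Beta(x, n−x+1) and the upper limit the 0.975 quantile of Beta(x+1, n−x). For x = 0 the upper limit is 1 − 0.025^(1/n).

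- n = 150: 1 − 0.025^(1/150) = 2.43%
- n = 50: 1 − 0.025^(1/50) = 7.11%

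Both match SAP 2.5.

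**Step 3: one excluded participant with the arm's only event, at planned arm sizes.**

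- Tablet: 1/50 = 2.0% (0.05 to 10.65) becomes 0/49 = 0% (0 to 7.25)
- Ring: 1/150 = 0.67% (0.02 to 3.66) becomes 0/149 = 0% (0 to 2.45)

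**Step 4: several events in the arm.** SAP 2.5 gives 197 enrolled pairs but not the split. At 3:1, 197 × 0.75 = 147.75 and 197 × 0.25 = 49.25, so 148 and 49 are assumed. The event counts are also assumed.

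| Arm | All dosed kept | One dropped, with event | One dropped, no event |
|---|---|---|---|
| Tablet | 3/49 = 6.12% (1.28 to 16.87) | 2/48 = 4.17% (0.51 to 14.25) | 3/48 = 6.25% (1.31 to 17.20) |
| Ring | 8/148 = 5.41% (2.36 to 10.37) | 7/147 = 4.76% (1.94 to 9.57) | 8/147 = 5.44% (2.38 to 10.44) |

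Dropping one participant with an event lowers the rate by 6.12 − 4.17 = 1.95 points (tablet) or 5.41 − 4.76 = 0.65 points (ring). Dropping one without an event raises it by 0.13 or 0.03 points.

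**Step 5: precision.** With no events, dropping five participants moves the upper limit from 7.25% (0/49) to 8.04% (0/44) in the tablet arm, and from 2.46% (0/148) to 2.55% (0/143) in the ring arm. The issue is which events are counted, not loss of sample size.

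**The case against.** The strongest reply is that eligibility is largely a matter of dated baseline facts. The HIV and pregnancy criteria refer to tests at Screening or Enrollment, and the laboratory criteria to Screening (protocol 5.2.1 and 5.3.1). A reader might infer that an HIV infection, pregnancy or abnormal laboratory value found during follow-up would make a participant retrospectively ineligible. The text does not support that: a mother who tested negative at entry met the criterion as written, and protocol 7.5.1 and 7.5.2 deal with later infection and pregnancy separately. This stands, and it confines the room for hindsight mainly to the judgement-based criteria.

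Four other stronger readings also go too far.

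- *Dosed participants are certain to leave the safety rates.* The at-least-one-dose sentence says the opposite. What is established is an unresolved contradiction, one side of which removes them.
- *Whole pairs are dropped.* The SAP says participants. Protocol 5.3.1 makes a mother ineligible if her infant is, but the SAP does not say whether one member's ineligibility removes the other from analysis.
- *The rates are biased downward.* That holds only if those dropped had events; otherwise the rate rises slightly.
- *The randomised comparison is broken.* The primary analysis is descriptive by arm, and adherence is stated to include all mothers.

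It can also be said that protocol 10.8.2 does not define its intent-to-treat set, so the conflict there is partly by silence. That is fair, but an exclusion from every analysis still needs to be declared, and it is not. The SAP change history comments on the intent-to-treat label; no weight is placed on that here.

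Finally, disclosure is already planned: SAP 6.5 tabulates and lists inappropriate enrollments, and the flow diagram in SAP 6.1 reports numbers analysed. Both show that such people exist. Neither returns their adverse events to the safety tables.

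**Conclusion.** The point holds as a conflict in the definition of the primary safety set. SAP 3.1 excludes participants found ineligible after enrollment from everything, without sparing those already exposed. That contradicts its own dosed-participant rule, SAP 7, SAP 9.1 and protocol 10.8.2. Followed literally, it could give a wrong safety rate, and no planned analysis would correct it.

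The actual size is unknown. The documents do not give the number found ineligible, which may be zero, or whether any had events. Under the assumed counts, each excluded participant with an event costs about 2 points in the tablet arm and about 0.65 points in the ring arm. If it is the arm's only event, the report changes from an event having occurred to none. If those excluded had no events, the effect is negligible and slightly upward. The documents do not show that any event was or will be lost; they show that the plan allows it.

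**What to change.** Delete the exclusion sentence from SAP 3.1 and replace it with a statement that:

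- all randomised participants stay in the ITT set under their assigned arm;
- all dosed mothers, and all infants of dosed mothers, stay in the primary safety set, whatever is later found about the eligibility of either member of the pair.

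If an eligible-only analysis is wanted, add it as a sensitivity analysis and report the numbers removed by arm with reasons. Ineligible enrollments are already to be tabulated under SAP 6.5, so nothing need be added there.

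The cost is one replaced passage in the SAP and, optionally, one extra table. No new data are needed. If nobody was found ineligible, the change alters no result.
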